## Sensitivity analysis 2: Matching-adjusted indirect comparison, external studies individually and combined

Overall survival

For each published study, the reconstructed IPD will be compared to the correspondingly weighted data from the DCVax®-L subjects. A Cox proportional hazards model will be used to estimate the treatment effect in the form of a hazard ratio.

Kaplan-Meier estimates of the survival functions for the weighted DCVax®-L population and the comparator population will be plotted and estimates of survival to 6, 12, 18, 24, 30, 36, 42, 48, 54 and 60 months will be calculated (with 95% confidence intervals).

Survival conditional on survival to M months

It may not be feasible to analyse conditional survival using this approach if the proportions of subjects with the relevant characteristics are not known for the subgroup surviving to at least M months unless the original data from comparator studies is available. If such data is available, this analysis will be conducted.

Overall survival for subgroups

It may not be feasible to analyse survival in subgroups using this approach if the proportions of subjects with the relevant characteristics are not known for the subgroups unless the original data from comparator studies is available. If such data is available, this analysis will be conducted.

Comparison of OS for treatments pooled across external studies

For each endpoint, the hazard ratio (HR) estimates and associated confidence intervals will be combined across the external study comparisons using a random effects meta-analysis (on the log scale) [18]. This combined HR estimate will include an upper confidence limit estimate at the relevant alpha level (see section 8.1.1).

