#### 1.2.1 Primary endpoint: OS compared with external controls – 3 analyses

**Analysis #1: Overall survival in the whole patient population**: This analysis will evaluate the overall survival curves and median survival for all of the patients in the Trial (both ITT and PP populations). This analysis will compare the survival times of the 232 patients initially randomized to DCVax®-L to the selected external controls. The comparisons will include the following:

- an overall comparison of the 232 patients to all external control patients, pooled;
- a matching-adjusted indirect comparison (MAIC) that takes into account the distribution of prognostic factors between the 232-patient DCVax®-L trial population and the external controls, pooled;
- a MAIC of the 232 patients to the control patients of each individual external control trial.

All comparisons will include an overall curve comparison, as well as comparisons of survival percentages at certain time points (so-called milestone analyses).

Analysis #2: Conditional survival -- the "long tail": This analysis will evaluate specifically the "long tail" of survival in patients treated with DCVax®-L in this Trial. With immunotherapies, one of the features most focused upon and considered most important clinically is their capability to deliver greatly extended survival in a percentage of patients. This analysis will apply an established statistical methodology – conditional survival – to evaluate the survival tail in this Trial separately from the larger picture. This methodology will evaluate all of the survival data relating to patients who survived beyond a specified time threshold. (This time threshold is the "condition" or trigger of the analysis). By analysing all of the data from the time threshold onwards, this methodology evaluates the whole survival tail and provides a more complete and representative assessment than a landmark analysis which would only evaluate the status of the survival tail at a specific time point.

**Analysis #3: Survival in pre-specified sub-groups:** It has become well recognized that GBM patients may be categorized into distinct sub-groups based upon certain patient characteristics and/or tumor characteristics, and these distinct sub-groups have materially different survival with GBM. Such

SAP Version: 1.0

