#### 8.1.3 External studies in newly diagnosed GBM

A systematic literature review has been conducted by independent experts to identify appropriate studies in newly diagnosed GBM to provide the external controls. This selection of studies has subsequently been reviewed by independent key opinion leaders in the field who were not involved in conducting the Trial, and has received their support. The five studies shown in Table 3 [6, 13-16], which were conducted in similar populations as in the current Phase III study, each with a control arm treated with the standard radiotherapy and temozolomide regimen, will be included. It is possible that additional studies may be added, e.g. with the goal to provide a larger population of patients with long (e.g.  $\geq$  4 years) follow-up times. In addition, a MAIC will be undertaken to ensure matching of the Trial subjects and the external controls.

It is recognized that each of these studies had unique inclusion and exclusion criteria, and that no single study can provide a perfectly matched control population. Nevertheless, the distribution of known prognostic factors between the enrolled patient populations reveal that these populations were similar in composition, and in fact the study outcomes are also remarkably similar: These five studies selected by the independent expert review provide 1,366 patients for the combined control group in total.

Median overall survival for these 1,366 patients is 16.5 months, with a 95% confidence interval of 16.0 to 17.5 months, demonstrating that outcome in this disease is highly consistent and predictable.

The Gilbert et al. (2014) study randomized patients 3 weeks prior to completion of chemoradiation therapy, and if that study is excluded from the analyses the outcomes of the control subjects are as follows: n=1,057; mOS=16.8 months (95% CI: 16.1-17.7 months).

Page 33 of 57 Confidential

Table 3: Studies selected providing comparable control arms

[figure not shown]
Lead	Year	Journal	CONT	ROL GROUP		
author			Treatment	N	Median OS (months)	OS Kaplan-Meier curves available for subgroups
Gilbert	2013	JCO	XRT + temozolomide	411	16.6	MGMT methylated (N = 122), unmethylated (N = 254)
Stupp	2017	JAMA	XRT + temozolomide	229	16.0	Age < 65y (N = 184), Age ≥ 65 y (N = 45),  MGMT methylated (N = 77),  unmethylated (N = 95)
Weller	2017	Lancet oncology	XRT + temozolomide	374	17.4	Minimal residual disease N = 210), Significant residual disease (N = 163)

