## **APPENDIX D: Matching-Adjusted Indirect Comparison**

Matching-adjusted indirect comparison (MAIC) is a technique that is commonly used to help inform cost-effectiveness modelling: an area where treatment effect estimates are frequently required for treatments not compared within the same trial or in trials with a common comparator treatment [32]. MAIC aims to adjust for differences in subject characteristics (both prognostic factors and treatment effect modifiers) between trials, in order to compensate for a lack of randomization, or imbalances between studies. Note that this method relies on the unverifiable assumption that outcomes can be fully predicted from the treatment and that all important prognostic factors and effect modifiers are included in the model [32].

Subject characteristics are identified that are reported in the current phase III study (Study 020221) and in the published data for the control arm. Subjects in the DCVax®-L arm of Study 020221 are then given weights such that overall the weighted averages of their characteristics match those of the control arm of the published study. Characteristics that can be included in some or all of these analyses, depending on what was reported for the control arm in question, are:

- MGMT methylation status
- Performance status
- Surgical status
- Age
- Sex
- Race

More specifically, it is assumed that we have a treatment  $k_1$  that has been studied in population  $s_1$  for which individual patient data (IPD) of covariates  $X_{s1} = \{x_i s_1\}$  are available, and a second population  $s_2$  where the treatment has not been studied, and where only the marginal means of the covariate data  $\overline{X}_{s_2}$  are available. The principle of the method is to translate the observed study results  $Y_{k_1s_1=\{y_i\}}$  in study population  $s_1$  to expected mean study results  $\widehat{Y}_{k_1s_2}$  by weighting the population in study  $s_1$  to make it more similar to population  $s_2$ . This is done using the following steps:

- 1) Re-centre the covariate vectors by subtracting  $\bar{X}_{S_2}$ , thereby generating two new vectors,  $X'_{S1}=X_{S1}-\bar{X}_{S_2}$  and  $\bar{X}'_{S_2}=0$
- 2) Find the values  $\hat{\alpha}$  that minimize  $\sum_{i=1}^{N_{s_1}} \exp(\alpha^T x_{is_1}')$ .
- 3) Apply survival analysis to the reweighted data.

Standard errors will be estimated using a robust sandwich estimator [33].

SAP Version: 1.0

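### Sensitivity analysis 2 pools hazard ratios that share the same 232 DCVax-L patients as if they were independent, so its combined confidence interval is too narrow

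*Combined protocol and SAP*

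**What the plan says.** SAP Section 1.2.1 lists, among the whole-population OS comparisons, "a MAIC of the 232 patients to the control patients of each individual external control trial". Section 8.1.5 (Sensitivity analysis 2) describes how: for each published study "the reconstructed IPD will be compared to the correspondingly weighted data from the DCVax®-L subjects", with a Cox model giving one hazard ratio per study. The last paragraph of that section states that, for each endpoint, the hazard ratios and their confidence intervals are "combined across the external study comparisons using a random effects meta-analysis (on the log scale) [18". It adds: "This combined HR estimate will include an upper confidence limit estimate at the relevant alpha level (see section 8.1.1".

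The only variance provision is in Appendix D: "Standard errors will be estimated using a robust sandwich estimator". That estimator works inside a single MAIC. I found no covariance between MAICs, no multivariate model and no joint resampling anywhere in the SAP or protocol. The footnote to Table 3 says that all analyses are run with and without the trial that randomized earlier, so the meta-analysis has five or four inputs for whole-population OS.

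**The concern.** The external control arms are different people, but the treated arm is the same 232 people each time, only re-weighted. If those patients happen to do better or worse than their expectation, every hazard ratio moves in the same direction. A meta-analysis that receives only hazard ratios and their intervals cannot see this. It treats the treated-arm error as separate draws and averages it down. The random-effects term does not repair this, because an error common to all the estimates does not make them differ and so adds nothing to Q or tau-squared.

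At stake is how strong the supporting evidence looks. Where only published data are available, the pooled Cox primary analysis is unadjusted, and the MAICs supply the prognostic matching on which the SAP relies. This combined figure summarizes the study-by-study MAICs and carries a limit at the Section 8.1.1 alpha (2% one-sided for OS), so it will naturally be read beside the primary result.

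**Working it through.** **Inputs.** Control-arm sizes are from SAP Table 3; the first two rows read "XRT + temozolomide 411 16.6" and "XRT + temozolomide 229 16.0". The treated arm is 232 (Section 1.2.1). The OS alpha is 2% one-sided (Section 8.1.1).

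**The plan's own figures.** 411 + 229 + 374 + 43 + 309 = 1,366, and 1,366 − 309 = 1,057. Both agree with Section 8.1.3. The SAP states no standard error for the meta-analysis.

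**Assumption.** Death counts are not given. I take 80% deaths in every arm as the base case and vary this over 60–90%. For orientation, the design figure is 233/348 = 67%.

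**Formulas, ignoring weights.** With d_T deaths in the treated arm and d_k in control arm k:

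- Var(log HR_k) = v_k = 1/d_T + 1/d_k
- Cov(log HR_j, log HR_k) = 1/d_T, because the treated arm is shared
- Reported variance of the pooled estimate = 1/Σ(1/v_k)
- Actual variance of the same estimate = 1/d_T + Σ(w_k²/d_k), with w_k = (1/v_k)/Σ(1/v_k)

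**Base case.** d_T = 0.8 × 232 = 185.6.

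| Control arm | N | d_k | v_k | 1/v_k | w_k |
|---|---|---|---|---|---|
| Dose-dense temozolomide trial | 411 | 328.8 | 0.00843 | 118.6 | 0.258 |
| Tumor-treating fields trial | 229 | 183.2 | 0.01085 | 92.2 | 0.200 |
| EGFRvIII vaccine trial | 374 | 299.2 | 0.00873 | 114.6 | 0.249 |
| Phase II dendritic cell vaccine trial | 43 | 34.4 | 0.03446 | 29.0 | 0.063 |
| First-line bevacizumab trial | 309 | 247.2 | 0.00943 | 106.0 | 0.230 |

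- Reported: Σ(1/v_k) = 460.4, so SE = √(1/460.4) = 0.047.
- Actual: 1/185.6 + 0.00096 = 0.00539 + 0.00096 = 0.00635, so SE = 0.080.
- Ratio: 0.0797/0.0466 = 1.71.
- One-sided 2% limit: z = 2.054, and 2.054/1.71 = 1.20, so the actual error is 11.5%. A 95% interval covers 75%.

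**Two checks.** A single pooled comparison that counts the 232 once has SE √(1/185.6 + 1/1,092.8) = 0.079, so the reported 0.047 reflects no extra information. Even if every patient in every arm had died, the unweighted treated arm alone would contribute √(1/232) = 0.066, while the reported pooled SE would be 0.042.

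**How the ratio moves.**

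| Setting | Ratio, actual SE to reported SE |
|---|---|
| Five studies, equal death fractions | 1.71 |
| Five studies, treated and control fractions varied separately, 60–90% | 1.60–1.81 |
| Four studies, equal fractions | 1.53 |
| Four studies, fractions varied separately | 1.45–1.62 |
| Simulated DerSimonian-Laird pooling, no heterogeneity | 1.68 |
| Same, true between-study SD 0.10 / 0.15 / 0.20 (log HR) | 1.56 / 1.38 / 1.25 |
| Simulated study-specific MAIC weights, mean effective sample size 154–222 | 1.52–1.58 |
| Same, mean effective sample size 108 | 1.31 |

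Section 8.1.5 names no between-study variance estimator; DerSimonian-Laird is my assumption. The MAIC simulation used four illustrative covariates, exponential survival and 800 runs per setting. Its actual one-sided error at nominal 2% ran from 10.5% down to 4.9%.

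**Likely heterogeneity.** The Table 3 medians (15.0–17.4 months), under an exponential approximation with 80% deaths, give Q of about 1.5 on 4 degrees of freedom across the control arms. Tau-squared would then probably be estimated as zero, as it was in 89% of the simulated meta-analyses without heterogeneity.

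**Effect on the limit (base case).** The upper limit is multiplied by exp(2.054 × (0.0466 − 0.0797)) = 0.934, so it is about 6.6% too low. At a combined HR of 0.80 it would be 0.880 instead of 0.942; both exclude 1. The reported limit excludes 1 below exp(−2.054 × 0.0466) = 0.91; the correct one does so below exp(−2.054 × 0.0797) = 0.85. The conclusion differs only between those values.

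**The case against.** The strongest reply is that little hangs on this step. It is the second of two sensitivity analyses. The primary pooled Cox model counts the 232 once, and so does the pooled MAIC of sensitivity analysis 1, so a matched comparison with all 1,366 controls is already planned without this fault. The individual-study MAICs are also sound on this point; only the final combination is wrong. The recurrent-disease MAICs in Section 8.2.3 specify no such pooling. All of this stands, and it limits the severity.

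The reply is also right about size. A factor of 1.6 to 1.7 could be read as fixed, but it needs five studies and little heterogeneity, and independence from the death fraction holds only when that fraction is equal in all arms. Section 8.1.3 allows further studies to be added, and conditional-survival and subgroup MAICs may not be feasible without original data. The figures therefore apply essentially to whole-population OS.

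A reader might infer from the reference to Section 8.1.1 that the combined hazard ratio is part of the success rule and that the trial's type I error is inflated. The text does not support that. It attaches a confidence limit to the estimate but no decision, and Section 8.1.5 ties the Figure 3 significance levels to the primary-analysis hazard ratios (the figure itself is not reproduced in the copy reviewed).

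What the reply does not remove is the direction: in every setting examined the reported interval is too narrow.

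**Conclusion.** The combination step is wrong as written. It ignores the covariance created by the shared treated arm, so the combined standard error is too small and the upper limit too low. For whole-population OS the actual standard error is about 1.7 times the reported one with five studies, equal death fractions and unweighted variances. It is about 1.5 times with four studies, and about 1.25 to 1.6 times with MAIC weighting or true heterogeneity. These factors rest on assumed death counts, illustrative weights and an assumed estimator of tau-squared. Even at 1.25 the nominal 2% error is about 5%.

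The consequence is that a supporting analysis could overstate its precision, and could appear to exclude 1 when it should not. It would be too strong to infer that it will falsely confirm the primary result: in the base case that can happen only for a combined hazard ratio of about 0.85 to 0.91. The error rates above belong to this supportive interval and not to the study's confirmatory tests. This should be fixed, but it does not threaten the primary analysis.

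**What to change.** Amend the last paragraph of sensitivity analysis 2 so that the confidence limit of the combined hazard ratio comes from one of two methods:

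- **Joint bootstrap.** In each replicate, resample the 232 DCVax-L patients once, resample the reconstructed control data within each study, refit every MAIC with the same resampled treated patients, and combine. The matching targets stay at their published values, since reconstructed survival data carry no covariates. Because this holds the set of studies fixed, the SAP should say how between-study variance enters the limit.
- **Multivariate random-effects model.** Supply the full covariance matrix of the log hazard ratios, with off-diagonal terms for the shared arm. These can be obtained from the bootstrap or from cross-products of each patient's contributions to the sandwich variances.

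The SAP should also name the between-study variance estimator and apply the same method to the four-study variant.

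The cost is one SAP paragraph, some programming and a wider combined interval. No new data are needed, and the SAP describes itself as preceding data lock and unblinding, so the change could be pre-specified.

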#### 8.1.6 Subgroup analyses for OS and CS

The analyses described for OS and CS will all be repeated for each of the following subgroups, where the data allow.

Table 5: Planned subgroup analyses

Characteristic	Subgroups		
Methylation status (MGMT):	Methylated, unmethylated		
• Extent of resection:	
 
Complete, partial
 
		
	
 
Significant, minimal residual
 
		
Age categories:	• 18-40, 41-50, 51-60, 61-64, ≥65		
• Sex:	
 
Male, female
 
		
• KPS:	

70 – 80, > 80 - 90, > 90 – 100

		

 
Baseline lymphocyte count (/μL):
 
	• ≤ median, > median		
	

≤ 1,000, > 1,000

		
	• ≤ 1,250, > 1,250		

 
RPA classification:
 
	
 
Class III, Class IV
 
		
• Race:	
 
Caucasian, non-Caucasian
 
		

 
Residual tumor size:
 
	
 
Measurement; also quartiles
 
		

 
PD-L1 expression in tumor tissue:
 
	

High, Low

		

 
PD-L1 status of circulating monocytes:
 
	
 
> 80% positive cells, ≤ 80%
 
		
	
 
> 50% positive cells, ≤ 50%
 
		
	
 
>10% positive cells, ≤ 10%
 
		

 
Pre-existing CD8 T-cell density:
 
	• ≤ median, > median		

 
Immunological responders to DCVax®-L:
 
	• Yes, No		

 
Histology - GBM subtype:
 
	
 
Proneural, Neural, Classical,
 
		
	Mesenchymal		
• Immunoscore:	• 0 through 5		
Biomarker status:	
 
EGFR and PTEN genes, IDH1 WT,
 
		
	1p19q intact		

 
Rapid progressors (subjects with PFS ≤ 2m):
 
			
	• Yes, No		

 
Early progressors: (subjects with PFS ≤ 4m):
 
	• Yes, No		

#### 8.2 Analysis for OS in recurrent GBM: comparison with external study control groups

This endpoint, will apply to those subjects who were originally assigned to the placebo arm and who received standard of care + placebo until disease progression, and who then crossed over to receive DCVax®-L post-progression. The survival of these subjects will be analyzed via comparison to external studies in recurrent GBM.

Secondary analyses will evaluate the same endpoint of OS post progression for the following populations:

<sup>10 For this study population: Class III: Age < 50 and KPS ≥ 90. Class IV: Age < 50 and KPS < 90, or Age ≥ 50.

- Patients who were originally assigned to DCVax®-L, and who received DCVax®-L under the crossover option following progression
- All patients, irrespective of original treatment assignment, who received DCVax®-L under the crossover option following progression

A systematic literature review for recurrent GBM studies has been conducted by independent experts to identify appropriate studies in recurrent GBM from which survival data for control groups could be obtained, in the same manner as the independent expert selection of the appropriate external studies for newly diagnosed GBM. The control patients from ten studies shown in Table 6 [5, 19-27], which were conducted in similar populations as in the current Phase III study, in trials which each had a control arm will be included. The control patients were treated with physician's choice of therapy or best available standard treatment, which could include standard treatments like lomustine or bevacizumab.

Table 6: Studies selected providing comparable control arms: recurrent GBM

Lead	Year	Journal	CONTROL GROUP		OS Kaplan-Meier curves	
author			Treatment arm	N	Median OS (months)	available for subgroups of interest
Brandes	2018	The Oncologist	Lomustine plus placebo	62	5.5	None
Wick	2017	NEJM	Lomustine	149	8.6	None
Wick	2010	JCO	Lomustine	92	7.1	None
Brandes	2016	Neuro- Oncology	Lomustine plus placebo	40	7.5	None
Lombardi	2019	Lancet Oncology	Lomustine	60	5.6	None
Taal	2014	Lancet Oncology	Best supportive care	30	8.0	None
Narita	2017	Neuro- Oncology	Lomustine	46	8.0	None
Cloughesy	2017	JCO	Bevacizumab plus placebo	65	12.6	MGMT methylated (N = 26), unmethylated (N = 25)
Galanis	2019	Cancer	Bevacizumab plus placebo	38	7.7	None
Lee	2020	Cancer	Bevacizumab plus placebo	58	11.5	None

Assuming original data are not available, the published Kaplan-Meier survival curves will be digitised and, along with the number at risk at each time (where available), will be used to re-construct the survival and censoring times (IPD) of the control arm subjects in the external studies using the Guyot method [17].

#### 8.2.1 Primary analysis: simple proportional hazards model

The primary analysis will be a comparison between the reconstructed individual patient data for all subjects, pooled across the external studies, with the subjects who crossed over from the placebo arm and were treated with DCVax®-L post-progression. Cox's proportional hazards model will be used.

Median survival and a 95% confidence interval will be reported.

The hazard ratio (HR) and a 95% confidence interval will be reported, as well as the associated 2-sided p value. Estimates of survival probability at 6, 12, 18, 24, 30, 36, 42, 48, 54 and 60 months will be calculated (with 95% confidence intervals).

Kaplan-Meier estimates of the survival functions for the DCVax®-L population and the comparator population will be plotted.

#### 8.2.2 Subgroup analyses

The same analysis will be repeated within the MGMT methylated and MGMT unmethylated subgroups. The individual patient data will be reconstructed from digitized KM plots for the single external study where the Kaplan-Meier curves are available for these subgroups.

